Growing evidence suggests that biofeedback interventions to modulate physiological, emotional, and behavioral stress responses are feasible, acceptable, and may reduce AUD symptoms such as craving to improve long-term AUD recovery. Our team extended this literature by conducting an exploratory pilot study among participants who had perpetrated IPV (N=4), and found that HRV biofeedback (HRV-B) conducted once daily for 10 days outperformed progressive muscle relaxation to restore normalized HRV. Taken together, this emerging data suggests that remote, self-administered biofeedback interventions hold promise as a discreet, accessible and low cost standalone or adjunct treatment option for AUD patients with high risk behaviors such as IPV. However, HRV has not yet been investigated as a mechanism of alcohol-facilitated IPV in naturalistic settings. Bridging this gap in the existing literature is essential to translate these promising laboratory findings into biomarker-driven treatment options to address this urgent public health problem. Thus, the primary objective of the proposed project is to use wearable technology to develop proof-of-concept of HRV as a biomarker of alcohol-facilitated IPV in naturalistic settings. Our secondary objective is to examine the preliminary usability, feasibility, and acceptability of a remote, self-administered HRV-B intervention.

To accomplish these goals, we will enroll a sample of 50 couples (100 total participants) with AUD and IPV into a 28-day micro-longitudinal study. Participants will wear activity trackers equipped with continuous ambulatory physiological monitoring and geolocation. Ecological momentary assessment (EMA; 4 times daily plus optional event-triggered reports) of alcohol use, couple conflict including IPV, and affect will be completed via smartphone application for 28 days. During days 22-28, participants will also be prompted to complete a 10 minute self-administered HRV-B session at least once daily. Subjective usability, feasibility, and acceptability of HRV-B will be assessed. The following Specific Aims are proposed:

**Specific Aim 1:** Employ a wearable physiological monitoring platform in combination with EMA and geolocation to examine the proximal role of HRV in alcohol-facilitated IPV among couples in naturalistic settings.

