**EMA Procedures.** Participants will download an application (provided by Illumivu, Inc.) on their mobile device. We will loan a compatible device and charger to participants who do not own one. Participants will complete a demo session (in person or via Doxy.me) with research staff to learn how to use the mobile device and EMA app and troubleshoot any challenges that arise. Four daily EMA reports will be requested via phone notification (Days 1-28; one morning report plus three subsequent reports at random times over the following 12 hours; i.e., one assessment per 4 hour time block). Participants will have the ability to select the time they receive the morning assessment and provide a daily window for start and end times. Both partners within each dyad will be assigned to the same assessment schedule. Participants will have 2 hours to complete the morning report and 30 minutes to complete subsequent reports, allowing flexibility to make up missed reports. Participants will also be instructed to complete event-driven reports if alcohol use or partner conflict occurs. Reports will include drinking and drug use, self and partner conflict behaviors, and subjective mood and affect. Research staff will contact participants by phone or text if the first two EMA entries on any particular day are missed.

**Physiological Assessment and Geolocation.** Participants will be issued a Garmin Vivosmart 4 activity tracker and charger and instructed to wear it continuously for 28 days of participation. We will instruct participants to charge the device during sleep to minimize disruption in data collection (60-90 minutes). No participant action is needed to store data from the tracker. EMA data is fully integrated with physiological data and geolocation using Illumivu's cloud-based server. This procedure will allow us to establish temporal sequence and both acute and lagged associations between HRV, drinking, and IPV, and to contextualize findings with geolocation. HRV measurements will be mean-centered for each participant in order to account for participants' baseline ("state"). *Illumivu, Inc. will provide cleaned data and peak, low, and average HRV for each 4-hour EMA assessment period.*

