## STATISTICAL ANALYSES.

**General.** All data will be collected in a REDCap database to ensure accuracy and validity and analyzed using SAS v9.4 (Cary, NC). Descriptive and summary statistics will characterize the sample and outcomes.

**Power and Sample Size.** Based on our enriched recruitment plan of couples with current AUD and IPV, and EMA studies of both healthy community couples and participants with IPV, we expect  $\geq 50\%$  of the couples enrolled in this study to report psychological or physical IPV during the 28-day study timeframe. Within-couple correlation of variables (HRV, alcohol use, IPV) will result in an effective sample size between  $N=50$  (the number of couples) and  $N=100$  (the number of individual participants). For example, for a within-couple intraclass correlation coefficient (ICC) of 0.1 or 0.3, sample sizes approximate  $N=90$  and  $N=76$ , respectively. At a minimum, the planned sample size conservatively provides 80% power to detect within-subject differences in HRV equivalent to Cohen's  $d$  effect sizes of 0.3 (the detectable difference with 1 paired set of observations on the  $\geq 50\%$  of subjects expected to report alcohol use and IPV), consistent with those observed in our preliminary studies (see Figure 1). However, given the volume of EMA data collected and despite the fact that many EMA reports will not involve alcohol or IPV, we may even be able to detect much smaller differences. For comparisons between partners within a dyad, we anticipate that effect sizes as small as 0.4 and correlations as small as 0.4 will be detectable with 80% power. Having  $N=100$  participants will also provide 85% power to detect whether feasibility and acceptability metrics are lower than 80%. These power analyses assume 2-sided testing and an alpha level of 0.05.

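### The stated 80% power for d = 0.3 does not follow from its stated inputs: 50 pairs detect d of about 0.40, and power at 0.3 is about 55%

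*Combined protocol and SAP*

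**What the plan says.** The statement is in Power and Sample Size, under Statistical Analyses. It is introduced as a minimum, and the claim for the HRV contrast reads: "the planned sample size conservatively provides 80% power to detect within-subject differences in HRV equivalent to".

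The size named there is a Cohen's d of 0.3. The plan explains that it rests on a single pair from each of the participants (half of them or more) who should record both drinking and IPV: "effect sizes of 0.3 (the detectable difference with 1 paired set of observations on the". On the test itself, the paragraph ends: "These power analyses assume 2-sided testing and an alpha level of 0.05".

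Three neighbouring statements matter:

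- On the volume of EMA data: "we may even be able to detect much smaller differences". Repeated windows are therefore offered as an improvement on 0.3.
- On the dyad comparison, again at 80% power: "For comparisons between partners within a dyad, we anticipate that effect sizes as small as 0.4".
- On clustering: within-couple ICCs of 0.1 and 0.3 are said to reduce 100 participants to effective sizes of about 90 and 76.

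The paragraph on Physiological Assessment and Geolocation describes an adjustment for each person's own level: "HRV measurements will be mean-centered for each participant in order to account for". It also says what the vendor supplies: "peak, low, and average HRV for each 4-hour EMA assessment period". The Specific Aims make HRV's role as a marker of IPV linked to drinking the central question: "the primary objective of the proposed project is to use wearable technology to develop proof-of-concept of HRV".

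**The concern.** A detectable effect for paired data depends on the number of pairs, alpha, power and the scale of d. The paragraph gives the first three and leaves the scale open. On the usual scale for a paired test (the SD of the differences), 50 pairs cannot detect 0.3 with 80% power. The same paragraph gives 0.4 for what is also a set of up to 50 pairs.

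This is the only power statement for the within-subject HRV contrast, and it is presented as a floor that extra data can only improve. A reader who judges a null result against 0.3, or who carries 0.3 into the planned R01, would rely on a figure that the described calculation does not give.

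**Working it through.** **Inputs, all from Power and Sample Size unless noted.** Two-sided alpha 0.05; power 80%; one pair per contributing participant; at least 50% of participants contribute; 100 participants in 50 couples (also in Human Subjects Involvement, Characteristics, and Design). Because the claim is worded as a minimum, the test case is n = 0.50 × 100 = 50 pairs.

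**Method.** Paired t-test, d = mean difference / SD of differences, df = n − 1, noncentral t with noncentrality d√n. Normal-approximation check: detectable d = (1.960 + 0.842)/√n.

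**Figures in the paragraph that do reproduce**

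- Effective sizes: 100/(1 + 0.1) = 90.9 and 100/(1 + 0.3) = 76.9, as stated.
- Dyad comparison: 50 pairs at d = 0.4 give 79.2% power, as stated after rounding.

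**The 0.3 figure, SD-of-differences scale**

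| Pairs | Detectable d at 80% power | Power at d = 0.3 |
|---|---|---|
| 50 (50% of participants) | 0.404 | 54.8% |
| 60 (60%) | 0.368 | 62.8% |
| 76 | 0.326 | 73.3% |
| 90 (90%) | 0.299 | 80.4% |

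Normal check at n = 50: 2.802/√50 = 0.396, power 56.4%. The number of pairs needed for d = 0.3 solves to 89.1 by the t-test, so 90. One-sided testing does not close the gap: at n = 50 the detectable d is 0.357 and power at 0.3 is 67.3%.

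The 0.3 matches about 90 pairs, which is also the effective size quoted for ICC 0.1 when all 100 participants contribute. That this was its source is only inference.

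**Raw-SD scale.** With within-person correlation ρ, detectable d = 0.404 × √(2(1 − ρ)):

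| ρ | 0 | 0.3 | 0.5 | 0.7 | 0.72 |
|---|---|---|---|---|---|
| Detectable d | 0.57 | 0.48 | 0.40 | 0.31 | 0.30 |

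Solving for 0.3: ρ = 1 − (0.3/0.404)²/2 = 0.72. If d were instead scaled by the within-person SD, which mean-centring makes a possible reading, uncorrelated windows give 0.404 × √2 = 0.57.

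**Repeated windows (assumptions: equal correlation, constant effect, independent participants).** One event window against the mean of k others: detectable d = 0.404 × √((1 + 1/k)/2).

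| k | 1 | 3 | 5 | 10 |
|---|---|---|---|---|
| Detectable d | 0.40 | 0.33 | 0.31 | 0.30 |
| Power at 0.3 | 55% | 72% | 77% | 80% |

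If 20% of the single-pair difference variance is true variation in the effect between participants, the variance factor at k = 10 is 0.2 + 0.8 × 0.55 = 0.64, and power falls to 74%.

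**Couple clustering (sensitivity only).** Suppose the 50 contributors are both partners of 25 couples. The effective number of pairs is 50/(1 + ICC), where the ICC is that of the differences, which the plan does not give:

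| ICC | Effective pairs | Detectable d | Power at 0.3 |
|---|---|---|---|
| 0.1 | 45.5 | 0.42 | 51% |
| 0.3 | 38.5 | 0.46 | 44% |
| 1 (extreme bound) | 25 | 0.58 | 30% |

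**The case against.** The best defence has three parts.

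**The scale is unstated, so the figure is unproven rather than wrong.** Cohen's d on the raw-SD scale gives 0.3 at a correlation of about 0.72. With 60% of participants contributing, the required value is about 0.67. Figure 1 is not visible in the public text and might bear on this. What stands: the documents do not exclude such a correlation. But the paragraph states neither the correlation nor the standardiser, and it cites Figure 1 for effects already observed, not for the detectable-effect calculation. An unstated favourable correlation cannot support a claim to be conservative.

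**The real design has far more than one pair.** Four reports a day for 28 days is 112 scheduled reports per person. Suppose each contributor has 2 event and 20 non-event windows (an assumption; the plan gives no event count). The variance factor is then (1/2 + 1/20)/2 = 0.275 and power at 0.3 is about 98%. It is about 89% with the 20% heterogeneity used above, and about 80% if a couple ICC of 0.3 is added. What stands: 0.3 may well be attainable in the full analysis, and 55% is not that analysis's power. But the plan defines 0.3 by one pair and then counts the EMA volume as further gain. The same data cannot do both.

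**This is a proof-of-concept study and the remedy is wording.** True, and the remedy below is limited accordingly. The number is still the stated power for the primary objective.

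**Conclusion.** The concern holds. On the inputs the plan gives (one pair on 50 of 100 participants, two-sided 0.05), the detectable effect at 80% power is about 0.40, not 0.3. Power at 0.3 is about 55%, some 25 points below the stated 80%.

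This result assumes d in SD-of-differences units and 50 independent participants. Positive correlation between partners' differences would make it worse. A raw-SD d with a within-person correlation of about 0.72 or more would rescue the figure, as would enough repeated windows, but neither is stated as its basis. The finding concerns the one-pair statement only. It does not show that the repeated-measures analysis is underpowered, because the plan does not quantify that analysis.

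**What to change.** Make one of two changes in Power and Sample Size.

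- **(a)** Restate the one-pair detectable effect as about 0.40 (SD-of-differences scale, 50 independent participants), and delete the wording that presents the figure as a minimum and as conservative.
- **(b)** Keep 0.3, and state the standardiser, the assumed within-person correlation, and the numbers of event and non-event EMA windows per participant that together give 80% power, with a justification for each.

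Option (b) is more informative because it describes the design that will be analysed. Under either option, add a sensitivity range for couple clustering of the within-subject differences. For the one-pair case this is 0.42 to 0.46 at ICC 0.1 to 0.3.

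The cost is text in one paragraph, with no change in enrolment or data collection. Under (a) the stated detectable effect becomes less favourable. Under (b) the added assumptions must be defended.

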**HRV-B Implementation.** Participants will be trained at baseline and then will be randomly prompted once daily on days 22-28 to complete 10 minutes of HRV-B according to published protocol. Participants will also be able to use HRV-B more often if they choose. HRV-B will guide participants in an evidence-based paced breathing technique (about 6 breaths per minute) using visualization on their mobile device of their real-time cardiac parameters. This process can reduce sympathetic dominance, enhance autonomic stability, and affect regulation, which cannot be accomplished by alternatives such as relaxation or deep breathing because participants must learn to breathe at their individualized cardiovascular resonant frequency.

**HRV-B Usability, Feasibility, and Acceptability.** We will assess the number of started, incomplete, and completed HRV-B sessions. Participants will be prompted twice at random intervals to respond to a brief survey assessing HRV-B: 1) ease of use, 2) willingness to continue use, 3) perceived helpfulness, 4) patient satisfaction, and 5) suggestions for modifications. In addition to providing subjective usability, feasibility, and acceptability at the exit interview, participants will complete the Website Analysis and Measurement Inventory (WAMMI), Post-Study System Usability Questionnaire (PSSUQ), and 8-item Client Satisfaction Questionnaire (CSQ). The investigators will discuss these outcomes and integrate participant suggestions for our planned R01 application.

**Compensation.** Participants will receive \$50 for the baseline assessment, \$1 per completed EMA report (\$112 maximum), a \$10 bonus for each week in which ≥80% of EMA reports are completed (\$40 maximum), \$10 for the purchase of the HRV4Biofeedback app, \$25 for completing all 4 weeks of participation, and \$25 for returning borrowed equipment (*return mailers provided*) for a possible \$252 total. Participants will be compensated via Clincard, or with check or cash.

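### The 85% power for feasibility and acceptability is quoted for 100 participants who are 50 couples, with no couple allowance, alternative rate or test stated

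*Combined protocol and SAP*

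**What the plan says.** Specific Aims sets the sample: "we will enroll a sample of 50 couples (100 total participants) with AUD and IPV into a 28-day micro-longitudinal study". It also places the biofeedback outcomes second: "Our secondary objective is to examine the preliminary usability, feasibility, and acceptability of a remote, self-administered HRV-B intervention".

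The Power and Sample Size paragraph of Statistical Analyses first deals with couples. It says "Within-couple correlation of variables (HRV, alcohol use, IPV) will result in an effective sample size between" 50 and 100, and that "for a within-couple intraclass correlation coefficient (ICC) of 0.1 or 0.3, sample sizes approximate" 90 and 76 respectively. Later in the same paragraph it says that 100 "participants will also provide 85% power to detect whether feasibility and acceptability metrics are lower than 80" per cent. It closes with "These power analyses assume 2-sided testing and an alpha level of 0.05".

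On analysis, the General paragraph says "Descriptive and summary statistics will characterize the sample and outcomes". The section on HRV-B usability, feasibility and acceptability describes how the results will be used: "The investigators will discuss these outcomes and integrate participant suggestions for our planned R01 application".

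**The concern.** By the plan's own range, 100 is the limit that applies when partners are uncorrelated. The feasibility figure is quoted at that limit, a few lines after the plan has explained why couples bring other variables below it.

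Correlation between partners is plausible for these metrics too. EMA Procedures puts both partners on the same assessment schedule, and HRV-B Implementation has everyone use biofeedback on days 22-28. If partners' use or ratings are positively correlated, power computed for 100 independent people is too high and an interval that ignores couples is too narrow. The results are meant to inform the planned R01 application, and Strengths and Limitations of Design lists statistical power among the things the findings will help to optimize there.

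The figure also cannot be checked as written, because power for a proportion needs two rates and the plan gives only one.

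**Working it through.** **Inputs from the plan.** 100 participants in 50 couples; reference rate 80%; two-sided alpha 0.05; example ICCs 0.1 and 0.3; stated power 85%. Not given: the alternative rate, the test, and an ICC for these metrics.

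**Step 1: the plan's effective sample sizes.** For clusters of two, effective N = 100/(1 + ICC). This gives 100/1.1 = 90.9 and 100/1.3 = 76.9, in line with the plan's 90 and 76.

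**Step 2: the 85% itself.** It cannot be rebuilt from stated inputs. Using power = Φ[(|p0 − p1|√n − 1.96√(p0(1 − p0))) / √(p1(1 − p1))] with p0 = 0.80 and n = 100, a true rate of p1 = 0.673 is needed to reach 85.0%. That rate is solved for, not taken from the plan.

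**Step 3: hold the alternative fixed and reduce n.** The second row is a check that needs no rates. A normal test with 85% power at n = 100 has noncentrality 1.960 + 1.036 = 2.996, which scales with √(n/100). The third row is another assumed pair of rates that gives about 85%.

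| Reading (two-sided 0.05) | n = 100 | n = 90 | n = 76 |
|---|---|---|---|
| 80% null, true 67.3% | 85.0% | 81.5% | 75.5% |
| Noncentrality 2.996 | 85.0% | 81.1% | 74.3% |
| 90% null, true 80% | 84.9% | 81.6% | 76.1% |

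So for a true rate below 80%, normal approximations give about 81-82% and 74-76%.

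**Step 4: how far other tests move this.** An exact binomial test solved to 85% at n = 100 (true rate 66.6%) gives 78.4% at 90 and 75.5% at 76; it moves unevenly because the counts are discrete. If the alternative lies above 80%, normal approximations give 79.5-81.1% at 90 and 69.1-74.3% at 76.

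**Step 5: could the 85% already allow for couples?** With the Step 2 formula, 80% against 65% at n = 76 gives 86.4%. An allowance already included is therefore possible.

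**Step 6: intervals.** For one binary outcome per participant at 80%, half-width = 1.96√(0.16/n): 7.8 points at 100, 8.3 at 90 and 9.0 at 76. A simulation of 50 couples at a true 80% (400,000 runs per ICC) compared a Wald interval that ignores couples with a couple-clustered interval (t, 49 df):

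| ICC | Coverage, couples ignored | Coverage, clustered | Mean half-width, clustered |
|---|---|---|---|
| 0 | 93.3% | 94.2% | 8.0 points |
| 0.1 | 92.0% | 93.9% | 8.4 points |
| 0.3 | 89.2% | 93.7% | 9.1 points |

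The Wald interval is already short of 95% at ICC 0. Ignoring couples therefore accounts for 93.3 − 92.0 = 1.3 points of the shortfall at ICC 0.1 and 93.3 − 89.2 = 4.1 points at ICC 0.3.

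**The case against.** The plan limits its couple correlation to HRV, alcohol use and IPV and offers 90 and 76 as examples. The shared schedule concerns EMA reports, whereas HRV-B prompts are random and sessions are self-administered, and only one partner per couple has to have AUD. The ICC for feasibility could be near zero or above 0.3. The reduced powers also depend on an alternative solved to fit the 85%. The metrics may not be one yes/no outcome per person, since sessions started, incomplete and completed are all counted. The study is a non-randomized pilot, and the supplied text states no go/no-go rule for these metrics.

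All of this stands, and it makes the point minor and conditional. It does not remove the gap: the figure is stated for 100 partnered people without the inputs needed to judge it.

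A reader might infer three stronger things that the documents do not support:

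- That the plan contradicts itself or has made an arithmetic error. It applies the couple reduction to other named variables, so there is no direct conflict.
- That no allowance was made. Only the absence of a stated allowance can be shown (Step 5).
- That no couple-adjusted analysis of these metrics exists. The supplied text states only descriptive summaries for them, but Strengths and Limitations of Design refers to earlier and exploratory analyses that do not appear in that text, so it may be abridged.

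**Conclusion.** The point holds as a minor, conditional one. The 85% is quoted for 100 participants in 50 couples with no couple allowance, alternative rate or test stated. Two assumptions set its size: that the 85% treats participants as independent, and that the plan's example ICCs carry over to these metrics. On both, with normal approximations and a true rate below 80%, power is about 81-82% at an effective 90 and 74-76% at 76. That is a loss of roughly 3-4 points and 9-11 points.

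These losses do not hold on every reading. The exact test in Step 4 loses 6.6 points at 90 (85.0 − 78.4), and alternatives above 80% can lose more than 11 points at 76. For intervals, ignoring couples would give about 92% or 89% coverage at ICC 0.1 or 0.3, against about 94% when clustered. Part of that gap comes from the Wald approximation.

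**What to change.** Restate the power sentence with everything it depends on. Suggested wording: For a true rate of [p1] against [p0], using [test], two-sided 0.05, power is [x]% with 100 independent participants and [y]% at an effective N of [n], assuming a within-couple ICC of [value] for these metrics. If the 85% already includes couple correlation, saying so and giving the ICC is enough for the power figure.

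Add to the analysis text: Each feasibility and acceptability proportion will be reported with a 95% confidence interval clustered by couple (50 clusters), and any test against 80% will use a couple-clustered standard error.

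The cost is wording and one recalculation, with no new data, visits or participants. The stated power may fall by a few points, more at ICC 0.3. Compared with the 7.8-point half-width that assumes independence, clustered intervals are wider by about 0.2 points if partners prove independent (8.0 − 7.8) and about 1.3 points at ICC 0.3 (9.1 − 7.8).

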**Specific Aim 2:** Conduct a non-randomized, open-label pilot study examining the usability, feasibility, and acceptability of a remote heart rate variability biofeedback (HRV-B) intervention to reduce alcohol-facilitated IPV.

We hypothesize that episodes of alcohol use and IPV will be characterized by lower HRV as compared to episodes when neither alcohol use nor IPV occurs. We also hypothesize that HRV-B will demonstrate usability, feasibility, and acceptability as evidenced by use at least once daily and positive self-reported feedback. This translational study will advance the mechanistic science in this area by examining the proximal role of HRV in alcohol-facilitated IPV in naturalistic settings. This study has the added benefit of utilizing discreet wearable technology and geolocation to refine and optimize the content, dose, and timing of HRV-B. Findings will facilitate

the development of urgently needed just-in-time interventions that are personalized, accessible, and dynamic. The investigative team has the unique expertise necessary to implement this innovative study, which has the potential to yield essential public health impact. Findings will directly inform the design of a randomized controlled trial testing the efficacy of HRV-B to reduce alcohol-facilitated IPV through R01 series funding.

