**Table 1. Eligibility Screening and Baseline Assessment Measures**

Instrument	Purpose	BSL	Exit	Daily
Breathalyzer Test	Screen for alcohol	X		
Urine Drug Test	Screen for drug use	X		
Pregnancy Test	Screen for pregnancy	X		
Breathalyzer Policy	Required document	X		
Participant Locator Form	Required document	X	X	
Participant Contact Form	Collect contact information	X		
Demographics Form	Collect demographics	X		
Participant History Form	Collect medical history and medications	X		
Adverse Events Form	Collect adverse Events		X	
EMA Morning Report	Collect daily substance use, partner conflict, mood and affect, device accessibility			X
EMA Random Report	Collect daily substance use, partner conflict, mood and affect, device accessibility			X
CIWA-Ar	Assess alcohol withdraw	X		
Mini Mental Status Exam (MMSE) 	Screen for cognitive deficits	X		
QuickSCID 	DSM-5 psychiatric disorders	X		
Traumatic Life Events Questionnaire (TLEQ) 	Assess trauma history	X		
Time Line Follow-Back 	Alcohol and drug use, IPV	X	X	
PTSD Checklist (PCL-5) 	Assess PTSD symptoms	X		
Beck Depression Inventory-II (BDI-II) 	Assess depression	X		
Alcohol Use Disorders Identification Test 	Alcohol problem severity	X		
Fagerstrom Test for Nicotine Dependence (FTND) 	Assess nicotine use	X		
Comprehensive Effects of Alcohol Questionnaire 	Alcohol expectancies	X		
Drinking Motives Questionnaire-Revised 	Drinking motives	X		
Revised Conflict Tactics Scale 	Intimate partner violence	X	X	
Dyadic Adjustment Scale-short form 	Relationship functioning	X	X	
State-Trait Anger Expression Inventory 	Trait anger	X		
Dissipation-Rumination Scale 	Hostile rumination	X		
Difficulties in Emotion Regulation Scale (DERS)	Assess Emotion Regulation	X		
Urgency, Premeditation, Perseverance, Sensation Seeking, Positive Urgency Impulsive Behavior Scale (UPPS-P)	Measure impulsivity	X		

HRV4Biofeedback Survey	Measure emotional state before and after breathing exercise during last 7 days			X
Breathing Prompt	Prompt breathing exercise during last 7 days			X
Website Analysis and Measurement Inventory 	Feasibility and Acceptability		X	
Post-Study System Usability Questionnaire 	Usability		X	
Client Satisfaction Questionnaire 	Client satisfaction		X	

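### Does the 80% feasibility benchmark need a named metric and a stated true rate before its 85% power can stand?

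*Combined protocol and SAP*

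**What the plan says.** Under Statistical Analyses, Power and Sample Size, the plan states that N=100 participants will provide "85% power to detect whether feasibility and acceptability metrics are lower than 80"%. The paragraph closes with "These power analyses assume 2-sided testing and an alpha level of 0.05". Earlier in it, couple clustering of HRV, alcohol use and IPV is allowed for: "for a within-couple intraclass correlation coefficient (ICC) of 0.1 or 0.3, sample sizes approximate" 90 and 76.

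The Specific Aims state the hypothesis without a percentage: "HRV-B will demonstrate usability, feasibility, and acceptability as evidenced by use at least once daily and positive self-reported feedback". Under HRV-B Implementation, participants are "randomly prompted once daily on days 22-28 to complete 10 minutes of HRV-B" and may use it more often if they wish. The next paragraph, on usability, feasibility and acceptability, says "We will assess the number of started, incomplete, and completed HRV-B sessions" and then lists a brief survey and three exit questionnaires. Table 1 gives one of these, the WAMMI, the purpose "Feasibility and Acceptability". The only other 80% in the document is the threshold for the EMA payment bonus, which does not concern the biofeedback.

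**The concern.** Feasibility is described in words in the Specific Aims, by session counts in the Approach, by a questionnaire in Table 1, and by a percentage in the power paragraph. Nothing links the percentage to the rest. Read literally, one prompt a day on days 22-28 makes daily use 7 days of 7. If the benchmark means 80% of prompted sessions, that is 0.80 × 7 = 5.6 sessions, so a participant at the benchmark would not have used the biofeedback every day. If it means 80% of participants using it every day, the bar is much higher. A metric left open could be chosen after the session counts are known.

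The power figure also lacks the input that every power figure needs, the true rate at which it holds. A reader might take 85% to cover modest shortfalls from 80%. The stakes are not nil, since the plan says "Findings will directly inform the design of a randomized controlled trial testing the efficacy of HRV-B".

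**Working it through.** **Inputs from the plan.** Benchmark p0 = 0.80; N = 100 participants (50 couples); two-sided alpha 0.05; 7 prompted days. The true rate p1, the correlation between one person's days and the expected completion rate are not given, so they are assumed below and shown as ranges. No dropout is assumed.

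**1. Can the 85% be reproduced?** Not forwards, because p1 is missing. Backwards, for a one-sample test of a participant-level proportion:

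Power = Φ{[p0 − 1.96·√(p0(1−p0)/N) − p1] / √(p1(1−p1)/N)}

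The rejection limit is 0.80 − 1.96 × √(0.80 × 0.20/100) = 0.80 − 0.0784 = 0.7216.

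- p1 = 0.673: (0.7216 − 0.673)/0.0469 = 1.04, power 85%.
- p1 = 0.70: power 68%.
- p1 = 0.75: (0.7216 − 0.75)/0.0433 = −0.66, power 26%.

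The exact binomial test (reject at 71 or fewer of 100) needs a true rate of 66.6% for 85% power and has 21% power at 75%. So the stated figure fits a true rate near 67%, about 13 points below the benchmark.

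**2. Would couple clustering overturn it?** The plan's effective sizes follow 100/(1 + ICC), which gives 90.9 and 76.9 for ICC 0.1 and 0.3. At p1 = 0.673 the power becomes 82% and 76%. The plan names HRV, alcohol use and IPV as the correlated variables, not biofeedback use, so applying these values here is an extension.

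**3. Do the two readings conflict?** Let m be the share of prompted sessions completed and r the within-person ICC. Under a beta-binomial model with a = m(1−r)/r and b = (1−m)(1−r)/r, the share of participants with use on all 7 days is the product over i = 0 to 6 of (a+i)/(a+b+i), or m⁷ when r = 0.

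| Sessions completed | r = 0 | r = 0.3 | r = 0.5 | r = 0.7 |
|---|---|---|---|---|
| 80% | 21% | 46% | 58% | 67% |
| 90% | 48% | 69% | 77% | 83% |
| 95% | 70% | 83% | 88% | 91% |

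In the first row the session reading sits on the benchmark (found below 80% in 1-2% of simulated studies). The all-days reading is found below 80% with probability 0.99 or more for r up to 0.5, and 0.67 to 0.85 for r = 0.7, depending on the test and the couple correlation. At 90% completion the answer turns on r. The all-days reading falls below 80% with probability 0.78 at r = 0.3 and 0.15 at r = 0.5 (partners independent), and at r = 0.7 its true value is above 80%. At 95% both readings exceed 80% from r = 0.3 upwards.

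**4. Do the sections contradict each other?** The 5.6-of-7 figure sets one person's count against a benchmark for a group, so it conflicts with daily use only if the session reading is assumed first. The power sentence counts participants, not up to 700 participant-days. Read as the share of participants with daily use, it is consistent with the Specific Aims. The pointer is not conclusive, because a mean of per-person completion rates also has N = 100.

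**5. Does Table 1 add a conflict?** No. The hypothesis names two strands of evidence, use and self-reported feedback. The Approach measures the first by session counts and the second by questionnaires. Table 1 lists instruments, so it is natural that the WAMMI carries the label there.

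**The case for a change.** The strongest case for a change is that it would be cheap and that feasibility is the whole question of Aim 2. The plan itself chose a benchmark, an alpha and a power, so it should say what they apply to. Illustrative data show the risk. Suppose 48 participants use the biofeedback on 7 days, 37 on 6, 12 on 5 and 3 on 4. Then 630 of 700 participant-days (90%) have use, but only 48 of 100 participants (95% CI 38% to 58%) used it every day. One rate is above 80%, the other clearly below.

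Much of this stands as description. The metric and the true rate are not written down, and nobody should read the 85% as covering a shortfall of a few points. What does not stand is the step from there to a defect. The data set is one choice among many, and the plan gives neither a completion rate nor a within-person correlation from which to judge it likely. Daily use as 7 of 7 is itself an inference, since an average of one session a day is another possible reading. No rule in the plan turns on crossing 80%: the investigators are to discuss these outcomes and draw on participants' suggestions for the next application. The section on strengths and limitations also refers to analyses that do not appear in the public text, so this text alone cannot establish that the metric was left open.

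**Conclusion.** No change is called for. The power sentence is terse: it omits the metric and the true rate. No stated rule or figure is shown to be wrong. The 85% matches a participant-level proportion with a true rate near 67%, tested two-sided at 0.05 with partners independent and no dropout. Couple correlations of 0.1 or 0.3, if they applied, would take it to 82% or 76%. The benchmark and the daily-use hypothesis agree under the reading that the sentence's own unit favours. The sharp disagreement between readings rests on assumed inputs and disappears at plausible alternatives.

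This is a secondary objective of a non-randomised pilot with no go/no-go threshold. The counts of started and completed sessions let an analyst report both the share of participants with use on all seven days and the share of prompted sessions completed, each with an interval. A reader planning the next trial would then have both figures, whichever one the 80% was meant for.
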